7.0 Study Design and Procedures

7.1 Study Design

Describe and explain the study design.

This research will utilize a randomized controlled trial (RCT) design. As this research includes three parenting programs, Incredible Years, PAT, and SafeCare, three RCTs will be conducted simultaneously. Randomization will occur at the site level to reduce the potential for contamination; as such, recruited parents will not be informed of the randomization process. When sites agree to participate (i.e., be randomized) they agree to implement the evidence-based parenting program plus the added module as they would typically implement the parenting program. Although the module is not evidence-based, they are agreeing to deliver as if it were standard procedure.

This section describes the design and procedures for the three RCTs: (1) *Incredible Years RCT*; (2) *Parents as Teachers RCT* and (3) *SafeCare RCT*. However, there are commonalities between the three trials:

- There will be two groups of providers— one assigned to deliver the parenting program and one assigned to deliver the parenting program plus additional SPSHK module at the end of the last session (described below), in support of the research question.
- Parents in the control group will complete assessments at four time points: pre-parenting intervention, post-parenting intervention, one-week post parenting, and one month post-intervention.
- Parents in the experimental group will complete assessments at four time points: pre-parenting intervention, post-parenting intervention, post-module, and one month post-intervention.
- For the experimental group, fidelity monitoring procedures will also occur in sessions for each enrolled provider-subjects. Parents and provider-subjects of these sessions will each complete a fidelity assessment instrument. With the parent’s permission, the provider will audio record two experimental sessions.

Different measures will be asked at specific assessment periods:

Measure Name (file name in supporting documents attachments)	Construct	Timing of Delivery (by Protocol Section description paragraph)
Alabama Parenting Questionnaire (APQ; ‘Measure_APQ.docx’)	Parenting behaviors and responding to child’s externalizing behaviors: subscales of Parental Involvement, Positive Parenting, Inconsistent Discipline Practices	7.2.1, 7.2.3, 7.2.5, 7.2.6

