8.2 Sample size determination

If applicable, provide a justification of the sample size outlined in section 8.1 – to include reflections on, or calculations of, the power of the study.

Parents as Teachers and SafeCare

In a two-arm RCT, sample size is determined by power and estimated effect size. We are doing a repeated measures design (4 assessments), so this must be accounted for in the sample size calculation. Assuming a desired power of .8 and estimated effect of .45, the sample size needed to detect an effect at alpha .05 is 62 individuals per group ($N = 124$) for each trial. That is, 124 participants for Parents as Teachers and 124 participants for SafeCare.

Incredible Years

Because the additive approach of our research is novel, we are relying on prior CSA prevention and general PE program research to estimate the effect size. A meta-analysis of general PE programs, from which CSA programs were excluded, found the estimated average effect size for trials including a control group to be $d = .3$. A meta-analysis of CSA-specific prevention programs (Davis & Gidycz, 2000) reported the average effect size for a single session program to be $d = .59$. Averaging these findings, we estimate the effect size of our module to be $d = .45$. The group-based delivery of IY requires the experimental design to be a cluster RCT and, as such, clustering must be considered in sample size calculation (i.e.,

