participants are nested within groups). In order to calculate the required sample size for the cluster randomized trials, we used the sample size calculation equation (Equation 1) for repeated measures from Heo and colleagues (2009; Equation 19, p. 385). Cluster sampling introduces a less precise estimate of parameters than simple random sampling (e.g., commonalities among participants); this increase of variance is estimated in the design effect ($2f$). Our design has repeated measures, which introduces autocorrelation (C_f); for our purposes we estimate this to be .7. Together, the design effect and the autocorrelation of the outcome of interest over time creates the corrected design effect ($2fC_f$), estimated to be 8.0025 for our calculation. Assuming $\alpha = .05$, $\beta = .80$, 10 participants per group (N_2), 3 measurement occasions (N_1), and an effect size (Δ) of 0.45, the number of groups needed per condition (N_3) is 11; this is in agreement with simulated sample sizes presented by Heo et al. (2009; Table 1). To account for participant attrition and lack of participation in research, **we will recruit 14 groups per condition such that our sample is comprised of ~ 280 participants (140 per condition).**

Equation 1.

$$N_3 = \frac{2fC_f(\phi^{-1}(1 - \frac{\alpha}{2}) + \phi^{-1}(1 - \beta))^2}{N_2N_1\Delta^2}$$

Fidelity

Other research indicates that two audio recorded sessions from 100 provider-subjects will be sufficient to answer fidelity research questions.

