17.0 Other Approvals

17.1 Other Approvals from External Entities

Describe any approvals that will be obtained prior to commencing the research (e.g., from cooperating institutions, community leaders, schools, external sites, funding agencies).

Agencies that implement Incredible Years or PAT or SafeCare parent-training programs will be approached by mail, email, and/or phone call and invited to participate in the study. Presentations or webinars will be made available to provide more information should agencies desire. Facilitators (i.e., the individuals who actually implement the programs with parents) will then be recruited and then randomized to either (a) business-as-usual implementation of their respective program or (b) implementation of their respective program and the additional, one-session CSA module. As we recruit sites to participate we will ask about their required approvals. At this time, no site that has agreed to participate has an external approval process. All they require is a letter from the PSU IRB saying this research is approved.

As a site is recruited, a document agreement will be acquired from someone in an oversight position who has a decision-making capacity over potential subjects.

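### Incredible Years is sized on parenting groups as independent units, with no term for the unit that is randomised; if a randomised site runs several groups, power is lower than Equation 1 implies.

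*Combined protocol and SAP*

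**What the plan says.** The sections describe the randomised unit differently.

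- Section 7.1: "Randomization will occur at the site level to reduce the potential for contamination". Section 4.1 agrees, describing experimental sites as those randomised to add the module.
- Section 17.1: "Facilitators (i.e., the individuals who actually implement the programs with parents) will then be recruited and then randomized".
- Section 8.1 counts parents as randomised, 140 to each Incredible Years arm.

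Section 8.2 justifies the design effect for Incredible Years with one level of clustering: "participants are nested within groups". It solves Equation 1 for the number of groups per condition, assuming "10 participants per group", three measurement occasions, an autocorrelation of .7, a corrected design effect of 8.0025 and an effect size of .45. The answer is 11. Because of attrition and non-participation, "we will recruit 14 groups per condition". No number of sites, number of groups per site, site correlation or attrition rate is given.

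Section 8.3 leaves the model open until recruitment is known. It mentions control for nesting only as a possibility, and lists simple t-tests, linear regression and hierarchical regression as candidates.

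**The concern.** The precision of the arm contrast in a cluster trial is governed by the number of independently allocated units. Equation 1 takes those units to be groups. Two groups at the same site receive the same allocation together and share an agency, so they are not two independent replicates of the randomisation.

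Two things follow when a site runs more than one group. First, any correlation between parents in different groups at the same site adds variance that Equation 1 omits. Second, even with no such correlation, the reference distribution should rest on the number of sites rather than the larger number of groups. Both lower power.

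If the analysis also ignores the site level, the first effect makes the standard error too small and the false-positive rate exceeds its nominal 5%. A t-test on individual parents, which section 8.3 permits, would ignore the group level as well.

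**Working it through.** **Reproducing the plan's figure.** Section 8.2 gives a corrected design effect of 8.0025, N2 = 10, N1 = 3 and Δ = .45, with a two-sided alpha of .05. The .80 printed as beta has to be read as power; taken literally it would give about 2 groups.

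N3 = 8.0025 × (1.960 + 0.842)² / (10 × 3 × .45²) = 8.0025 × 7.849 / 6.075 = 10.34, rounded up to 11. This agrees with the plan. Power at 11 groups is .82 by the normal approximation.

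**Back-solving the design effect.** The plan does not print a within-group correlation. The value 8.0025 equals 2 × 3.75 × 1.067 exactly, with 3.75 = 1 + 3 × 9 × .05 + 2 × .7. I therefore use a within-group correlation of .05 and a factor of 1.067. Both are inferred, not stated.

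**Adding the site level.** Let m be parents analysed per group, k groups per site, and r the correlation between parents in different groups at the same site. The design effect becomes

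c = 2 × 1.067 × [1 + 2 × .7 + 3(m − 1) × .05 + 3m(k − 1)r].

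With 14 groups per arm, the non-centrality is √(14 × m × 3 × .45² / c). Power comes from a non-central t with 2(14/k − 1) degrees of freedom: 26 for k = 1 and 12 for k = 2.

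**Assumptions on k, r and attrition.** I show k = 1 and k = 2. I take r from 0 to .05; .05 is an upper bound, because there all the within-group correlation comes from the site. For attrition I take 110 analysed parents per arm (11 × 10, the calculated requirement), so m = 110/14 = 7.857, a loss of 30/140 = 21%. Full retention has m = 10.

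**Worked case.** For m = 7.857, k = 2 and r = .025:

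c = 2.134 × [2.4 + 1.0286 + 0.5893] = 8.574. Non-centrality = √(66.825 / 8.574) = 2.79. With 12 degrees of freedom, power is .727.

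| Groups per site | r | Power, 110 per arm | Power, full retention |
|---|---|---|---|
| 1 | not applicable | .83 | .88 |
| 2 | 0 | .79 | .85 |
| 2 | .01 | .77 | .82 |
| 2 | .025 | .73 | .78 |
| 2 | .05 | .67 | .72 |

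**Type I error of a group-only test.** The ratio of the true to the assumed standard error is √(c at k = 2 / c at k = 1). With 110 per arm it is 1.034, 1.083 and 1.159 for r = .01, .025 and .05. The true error rate of a nominal 5% test, 2[1 − Φ(1.96/ratio)], is then 5.8%, 7.0% and 9.1%. This uses a normal reference, so it shows the effect of the omitted variance alone, not of the degrees of freedom.

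**The case against.** A reader might infer that the trial is underpowered and that its intervals will be too narrow. The documents do not support either as a fact.

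- **Groups per site is unknown.** Nothing shows that any site will run two groups. With one group per site, the group is the randomised unit and section 8.2 stands.
- **The randomised unit is unsettled.** If section 17.1 governs and each facilitator runs one group, the site argument changes. But a facilitator who leads two groups gives both the same allocation, so section 17.1 does not by itself rescue the calculation.
- **No group-only model is specified.** Section 8.3 ties the choice of model to the participating sites and includes hierarchical regression. The type I error figures belong to an analysis that the plan allows but does not choose.
- **The mild cases are close to target.** With two groups per site and r = .01, power is 82% at full retention and 77% after the assumed attrition. Part of the fall from one group per site is due to degrees of freedom, not to correlation: 83% to 79% at r = 0.
- **There is a margin.** Fourteen groups are recruited where 11 are needed. Section 8.2 assigns that margin to attrition and non-participation, however, so it cannot also be counted as cover for site clustering.

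These objections limit the size of the problem and make it conditional. They leave the mismatch between sections 7.1, 8.2 and 17.1 in place, and they do not supply the missing commitment in section 8.3.

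**Conclusion.** The mismatch stands with high confidence: the randomised unit is named inconsistently, the Incredible Years sample size has no term for it, and the analysis is not tied to it.

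Confidence in the size is moderate. The consequence ranges from nothing, at one group per site, to power of about 67% against the planned 80%, at two groups per site with the upper-bound correlation and attrition to 110 per arm. Inflated type I error arises only if the analysis stops below the randomised unit. All the percentages beyond the plan's own 11 groups are illustrative. They rest on the back-solved correlation and factor, the assumed attrition, and site figures that the documents do not give.

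**What to change.** - **Sections 7.1, 8.1 and 17.1:** name the same unit of randomisation.
- **Section 8.3:** commit to a model with the randomised unit as the top-level random effect, and take degrees of freedom from the number of randomised units. Add group within that unit only where a unit runs more than one group; if every unit runs a single group, the two variances cannot be separated. Remove simple t-tests on parents for Incredible Years.
- **Section 8.2:** state the expected number of sites and groups per site, and restate power over a range of same-site correlations, including a low value such as .01.

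The cost is wording and, where sites run several groups, one more variance term. The stated power becomes less favourable and intervals may widen. No extra parents are needed to make the change, but it reports the power honestly rather than restoring it. It should be settled before outcome data are seen.

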8.3 Statistical methods

Describe the statistical methods (or non-statistical methods of analysis) that will be employed.

We will be examining the effect of our module using a variety of statistical methods. Exact models to be used will be dictated by recruitment and participating sites (e.g., potentially controlling for nesting). Statistical methods considered will include simple t-tests, general linear regression models, or hierarchical regression models. We are powered for repeated measure ANOVA between factors.

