4.0 Recruitment Methods

4.1 Identification of subjects

Describe the methods that will be used to identify potential subjects or the source of the subjects. If not recruiting subjects directly (e.g., database query for eligible records or samples) state what will be queried, how and by whom.

StudyFinder: If you intend to use StudyFinder (<http://studyfinder.psu.edu>) for recruitment purposes, please indicate this in section 4.1 along with any other methods for identifying subjects. Note that information provided in this protocol should be consistent with information provided on the StudyFinder page in your CATS IRB study.

For Penn State Hershey submissions using Enterprise Information Management (EIM) for recruitment, attach your EIM Design Specification form on the Basic Information page in CATS IRB (<http://irb.psu.edu>). See HRP-103 Investigator Manual, "What is appropriate for study recruitment?" for additional information.

We will utilize our relationship with community partners (i.e., providers of the parent-education programs) and Children and Youth agencies to recruit provider agencies.

After obtaining provider buy-in at both experimental and control sites, we will recruit participants directly through providers at these agencies.

For experimental sites, that is those who are randomized to add the CSA module onto the existing PE program, providers will be recruited to participate in the fidelity research at the time of training in SPSHK.

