7.2.1 Pre-parenting Intervention Assessment

Provide a description as defined above and format accordingly.

As described above, parents are recruited to participation in the research after independently signing up to participate in Incredible Years, Parents as Teachers, or SafeCare, and the agency/site providing their parenting program would have already agreed to randomization (and experimental condition providers received their training in the SPSHK module). Following consent and before any intervention has occurred, the parents will be given a paper copy of the assessment. A member of the research team will distribute surveys (identified only by a unique code—see Section 9) at the beginning of the first session to parents who have consented to participate.

The assessment is given in a booklet format. At this assessment point, parent survey booklets include the APQ, AUDIT, CES-D, DAST, ISEL-SF, READI-SF, a demographics questionnaire, and the module assessment of parents’ attitudes, knowledge, and behaviors of CSA prevention (measures described above in Section 7.1). Providers in the group sessions (Incredible Years) will engage with parents who do not wish to participate separately at this time.

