8.0 Subject Numbers and Statistical Plan

8.1 Number of Subjects

Indicate the total number of subjects to be accrued.

If applicable, distinguish between the number of subjects who are expected to be enrolled and screened, and the number of subjects needed to complete the research procedures (i.e., numbers of subjects excluding screen failures.)

The number of subjects needed for the PAT randomized controlled trial is 124: 62 randomized to the control group, 62 randomized to the experimental group.

The number of subjects needed for the SafeCare randomized controlled trial is 124: 62 randomized to the control group, 62 randomized to the experimental group.

The number of subjects needed for the Incredible Years cluster randomized controlled trial is 280: 140 randomized to the control group, 140 randomized to the experimental group.

We expect to enroll approximately 100 provider-subjects for the fidelity research.

In total we expect to enroll 628 subjects, both parent and provider-subjects.

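### Section 8.3 makes adjustment for clustering optional although all three trials allocate parents in clusters, and the PAT and SafeCare sample size has no clustering term

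*Combined protocol and SAP*

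**What the plan says.** Section 7.1, under the design common to all three trials, states: "Randomization will occur at the site level to reduce the potential for contamination". Section 4.1 agrees: "For experimental sites, that is those who are randomized to add the CSA module onto the existing PE program". Section 7.2.1 says that "the agency/site providing their parenting program would have already agreed to randomization", which fits but does not itself name the unit. Section 17.1 differs: "Facilitators (i.e., the individuals who actually implement the programs with parents) will then be recruited and then randomized to either" usual implementation or implementation with the added module.

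Section 8.1 gives the cluster label to one trial only. For Incredible Years (IY) it reads "The number of subjects needed for the Incredible Years cluster randomized controlled trial is 280"; for PAT, "The number of subjects needed for the PAT randomized controlled trial is 124: 62 randomized to the control group"; SafeCare has the same numbers as PAT. Section 8.2 builds clustering into the IY calculation and not into the other two.

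The analysis plan is the single paragraph of section 8.3. On nesting it says "Exact models to be used will be dictated by recruitment and participating sites (e.g., potentially controlling for nesting". The methods are then listed: "Statistical methods considered will include simple t-tests, general linear regression models, or hierarchical regression models". It adds that the study is powered for a between-factor repeated-measures ANOVA. Section 1.2 names the Module Assessment as the primary outcome. No section says which of the four assessments (T1 to T4), or which contrast, tests hypothesis (b), the comparison between arms.

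**The concern.** Whether sites or facilitators are randomised, parents who share a unit share an arm. A test that treats those parents as independent understates the standard error of the arm difference unless cluster effects are negligible or cancel in the chosen contrast. The documents give no ICC, site count or site size to show that either is so. Under 8.3 as written, an unclustered t-test or regression complies with the plan, and the model can be chosen after recruitment is known. Nothing directs PAT or SafeCare to a clustered analysis.

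The contrast matters too. T1 and T2 precede the module (sections 7.2.1, 7.2.3 and 7.2.4), so a T3 comparison, a change from T1 and a four-occasion mean are not equivalent, and clustering affects them differently. At stake are the error rate of the trials' main claim and the stated 80% power for PAT and SafeCare. Hypothesis (a), change within the experimental arm, is not at issue here.

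**Working it through.** **Inputs from the protocol.** Alpha .05, effect .45, power .80, 62 per arm and four assessments for PAT and SafeCare; 140 per arm, 10 per group, 14 groups per arm (11 required), three occasions, autocorrelation .7 and corrected design effect 8.0025 for IY; about 100 provider-subjects.

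**Assumptions.** ICC .01 to .10; cluster size m of 5 to 31 (10 is documented only for IY groups; 31 means two clusters per arm in PAT or SafeCare); within-person correlation .7 (stated only for IY); two-sided tests.

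**1. The plan's own figures.**
- IY, Equation 1: 8.0025 × (1.960 + 0.842)² / (10 × 3 × 0.45²) = 10.34, so 11 groups, as stated. This reads the protocol's β of .80 as power.
- PAT and SafeCare, between-factor test over four occasions: the variance factor is (1 + 3 × .7)/4 = .775 and the noncentrality is (.45/2)² × 124/.775 = 8.10. Power is .806 at 62 per arm and just under .80 at 61. The figure of 62 is therefore reached with no clustering term.

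**2. Unclustered t-test on post-module scores.** False-positive rate = 2[1 − Φ(1.96/√DE)], with DE = 1 + (m − 1) × ICC. At ICC .05 and m = 10, DE = 1.45 and the rate is 10.4%.

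| ICC | m = 5 | m = 10 | m = 20 | m = 31 |
|---|---|---|---|---|
| .01 | 5.5% | 6.0% | 7.2% | 8.6% |
| .05 | 7.4% | 10.4% | 16.0% | 21.5% |
| .10 | 9.8% | 15.5% | 25.0% | 32.7% |

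Simulation agrees within about one percentage point.

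**3. Between-factor repeated-measures test, the one 8.3 names.** Over four occasions the ignored variance ratio is [3.1 + 4(m − 1)ICC]/3.1 if site effects are stable over time, and [3.1 + (m − 1)ICC]/3.1 if they are independent at each occasion, where 3.1 = 1 + 3 × .7. At ICC .05 and m = 10:
- stable: (3.1 + 1.8)/3.1 = 1.58, rate 11.9%;
- time-specific: (3.1 + 0.45)/3.1 = 1.145, rate 6.7%.

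**4. Unclustered tests that use T1.** Simulated with 6 clusters of 10 per arm at ICC .05:

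| Site effects from T1 to T3 | Regression on T1 | Change score |
|---|---|---|
| Stable | 5.9% | 4.9% |
| Half time-specific | 13.0% | 13.7% |
| Fully time-specific | 18.3% | 20.3% |

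Baseline adjustment protects only in the first row. Cluster-level tests held 4.6% to 5.6% over 2 to 14 clusters per arm and ICC .01 to .10.

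**5. If facilitators are randomised.** Sections 3.1 and 3.2 restrict provider-subjects to those trained in and delivering the module. Experimental parents number 62 + 62 + 140 = 264, and 264/100 ≈ 2.6 per provider. The step 2 formula at m = 2.6 gives about 5.2%, 6.0% and 6.9% at ICC .01, .05 and .10. This averages over three trials; IY groups are larger, so PAT and SafeCare would average less.

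**6. Power for PAT and SafeCare at effect .45 and ICC .05.** For the four-occasion mean, the variance of the arm difference is (2/62)[3.1 + k(m − 1)ICC]/4, with k = 4 (stable) or 1 (time-specific), referred to t on clusters minus 2 degrees of freedom. At 6 × 10 and stable effects, the variance is .0395, .45/√.0395 = 2.26 and the critical value is 2.23, so power is .53.

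| Clusters × parents per arm | Stable | Time-specific |
|---|---|---|
| 12 × 5 | .68 | .75 |
| 6 × 10 | .53 | .67 |
| 3 × 20 | .31 | .47 |

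For T3 adjusted for T1 with a cluster-level test at 6 × 10, simulated power is about .85, .67 and .53 for stable, half and fully time-specific site effects (the stable value varied by about .02 between simulations).

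**The case against.** Section 8.3 lists hierarchical regression, mentions nesting and leaves room for a correct analysis, and section 8.2 shows that the authors knew clustering mattered for IY. That stands. A reader might infer that the plan commits to an invalid test or ignores clustering altogether. The documents do not support that: the defect is that adjustment is optional.

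Section 8.3 also does not assign the t-test to the between-arm comparison or to post-module scores; it could be meant for hypothesis (a). That stands too, so the 10% figure is a scenario. But nothing in 8.3 confines the t-test to hypothesis (a), and the repeated-measures test that it does tie to the design is also inflated if run without a cluster term.

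The cluster sizes of 5 to 31 describe sites or groups. On the facilitator reading in section 17.1 the inflation could be slight. This limits the size of the problem on that reading but does not remove it, because sections 4.1 and 7.1 say sites.

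Home delivery in PAT and SafeCare is no answer: individual visits do not undo allocation by site or facilitator.

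**Conclusion.** The point holds and should be fixed before analysis. All three trials allocate clusters, 8.3 does not require the between-arm test to reflect that, and the 62 per arm omits it.

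The size is uncertain. For site- or group-sized clusters at ICC .05 and 10 per cluster, false positives are about 10% for a post-module t-test, and about 12% or 7% for the between-factor test. Over the assumed ranges the t-test runs from 5.5% to 33%, the top being an extreme with two clusters per arm. With facilitators randomised it is about 5.2% to 6.9%. A reader might infer that the trials' error rate is doubled; without an ICC, a site size or a settled unit, the documents do not establish that.

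Nor do they establish that IY is safe. Its 14 groups of 10 describe the randomised units only if each randomised site runs a single group. On that condition, T3 adjusted for T1 with 11 groups per arm has simulated power of .99, .92 and .82 (stable, half and fully time-specific site effects, ICC .05). If sites run several groups, that reassurance lapses.

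**What to change.** In section 8.3:
- Name one primary between-arm contrast per trial, for example the T3 Module Assessment adjusted for T1.
- Require either a mixed model with a random effect for the randomised unit (plus group within site for IY) and a small-sample correction, or a cluster-level test of baseline-adjusted cluster means. With few clusters the cluster-level test is the safer choice: a mixed model using t on clusters minus 2 degrees of freedom rejected only 0.7% of the time under the null at 3 clusters of 20 per arm, ICC .05 and stable site effects. Kenward-Roger is one possible correction but was not the one simulated.
- Remove simple t-tests and unclustered regression for this comparison.

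Elsewhere, reconcile sections 4.1 and 7.1 (sites) with section 17.1 (facilitators), so that the model matches the unit randomised. Restate the PAT and SafeCare power in section 8.2 for the chosen contrast, with a clustering term and cluster degrees of freedom.

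The cost is a rewritten paragraph, a revised power statement, and site, facilitator and group codes on each parent record. No extra parents are requested. Confidence intervals will be wider and the stated power less favourable.

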1.0 Objectives

1.1 Study Objectives

Describe the purpose, specific aims or objectives. State the hypotheses to be tested.

The purpose of the proposed study is to assess the effectiveness of the addition of a single-session child sexual abuse (CSA) prevention module (*Smart Parents – Safe and Healthy Kids*) on improving parents' knowledge, attitudes, and behaviors regarding CSA prevention for parents already receiving parent-education services (e.g., The Incredible Years, Parents as Teachers, SafeCare). We hypothesize that parents who receive the parenting curriculum and the CSA prevention module will (a) demonstrate significant improvement in CSA-related knowledge, attitudes, and protective behaviors from pre-test to post-test, and (b) demonstrate higher scores on CSA-related knowledge, attitudes, and protective behaviors as compared to parents who only receive the parenting curriculum.

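### Section 8.3 does not make the T1 Module Assessment a covariate in the between-arm comparison: it permits a t-test that ignores T1, and its powered test averages T1 in as an outcome

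*Combined protocol and SAP*

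**What the plan says.** Section 1.1 states two hypotheses. The first is within-arm: parents given the module will "demonstrate significant improvement in CSA-related knowledge, attitudes, and protective behaviors from pre-test to post-test". The second is between-arm: they will "demonstrate higher scores on CSA-related knowledge, attitudes, and protective behaviors as compared to parents who only receive the parenting curriculum". Baseline enters the first and is not mentioned in the second.

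Section 8.3 does not choose a model. "Statistical methods considered will include simple t-tests, general linear regression models, or hierarchical regression models", and "Exact models to be used will be dictated by recruitment and participating sites (e.g., potentially controlling for nesting"). It adds: "We are powered for repeated measure ANOVA between factors". It names no covariate and no primary time point.

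The baseline score exists. Under 7.2.1, "Following consent and before any intervention has occurred, the parents will be given a paper copy of the assessment", and that booklet includes the Module Assessment, which 1.2 names as the primary outcome. The same instrument is repeated at T2 (end of the parenting programme), T3 (after the module, or one week later for controls) and T4 (one month on). Under 7.2.4 the module is delivered in the week after T2.

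Section 8.2 sizes PAT and SafeCare at 62 per group for an effect of .45 with four assessments. For Incredible Years it gives a correlation over time: "for our purposes we estimate this to be .7".

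**The concern.** The pre-programme value of the primary outcome is usually the strongest single predictor of the later value. Putting it in the model as a covariate takes the variance it explains out of the error term. It also corrects the arm difference for the part of any baseline gap that carries through to follow-up. Section 7.1 allocates sites, so a trial with few sites can easily start with unequal arms.

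Two of the analyses in 8.3 do not use T1 in this way. A t-test on a post-module score discards it. The between-factors test in a repeated-measures ANOVA compares arm means over all occasions, so T1 and T2, which precede the module, are averaged in with T3 and T4. That adds occasions on which no module effect is expected. A regression could include T1, but 8.3 does not say that it will. If the model is settled after recruitment, the choice between adjusted and unadjusted results also stays open.

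At stake are power at the planned sample size and the size of the chance error that baseline differences can add to the estimate.

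**Working it through.** **Inputs from the documents.** d = .45, alpha .05, power .80, 62 per group, 4 assessments (8.2, PAT and SafeCare); correlation over time .7 (8.2, Incredible Years only); module delivered after T2 (7.2.4). The tests are taken as two-sided, as in Equation 1.

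**Assumptions.** The T1-to-post correlation r is taken as .7, .5 and .34. The last is .7 cubed, which is the T1-to-T4 value if correlation decays by .7 per occasion. Clustering is ignored in steps 1 to 3.

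**1. The plan's own figure.** For the between-factors test, f = d/2 = .225 and the noncentrality is N f² m / (1 + (m − 1)r). With N = 124, m = 4 and r = .7 this is 124 × .050625 × 4 / 3.1 = 8.10, and power is 80.6%. The smallest even N that reaches 80% is 124, which matches the plan. So .7 may also lie behind the PAT and SafeCare numbers, but 8.2 does not say so.

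**2. The same test if the effect appears only after the module.** A difference of .45 at T3 and T4 and zero at T1 and T2 averages to .225. The variance of a four-occasion mean is (1 + 3 × .7)/4 = .775. The noncentrality is .225 / √(2 × .775/62) = 1.42, and power is about 29%.

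**3. One post-module score, with and without T1.** The noncentrality is .45 / √(2(1 − r²)/62), with power from the noncentral t distribution.

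| Analysis | Variance factor 1 − r² | SE factor | Noncentrality | Power |
|---|---|---|---|---|
| Unadjusted | 1.00 | 1.00 | 2.51 | 70% |
| T1 covariate, r = .34 | .88 | .94 | 2.66 | 75% |
| T1 covariate, r = .5 | .75 | .87 | 2.89 | 82% |
| T1 covariate, r = .7 | .51 | .71 | 3.51 | 94% |

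By the normal approximation, 80% power needs 78 per group unadjusted and 40 per group adjusted at r = .7.

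**4. Clustering.** The documents give neither the number of sites nor an intraclass correlation (ICC). Two assumed cases show how far the absolute figures move:

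- ICC .05 and 10 parents per site: design effect 1 + 9 × .05 = 1.45. Power is 54% unadjusted and 82% adjusted at r = .7 (66% at .5, 59% at .34), with individual-level degrees of freedom.
- ICC .05 and 8 sites of unequal size (mean 124/8 = 15.5, coefficient of variation .6): design effect 1 + (1.36 × 15.5 − 1) × .05 = 2.00. With 8 − 2 = 6 degrees of freedom, power is about 32% unadjusted and 55% adjusted at r = .7.

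Adjustment gains power in both cases, but in the second it does not reach 80%.

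**5. Incredible Years.** For means of 10-parent groups with an assumed ICC of .05 and individual-level r = .7, let c be the correlation between group-level effects at T1 and post-module. The adjusted-to-unadjusted variance ratio is [.05(1 − c²) + .95 × .51/10] / [.05 + .95/10]. This is .51 at c = .7, .40 at c = .9 and .68 at c = 0.

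**The case against.** The strongest reply is that 8.3 does not propose an unadjusted analysis. It lists methods under consideration, and both regression families can take a T1 covariate. That stands. A reader might infer that the plan has chosen to compare raw post-module scores; the text does not support this. The point is that T1 adjustment is not specified, and that an option which ignores T1 remains open.

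A second reply is that the largest gain rests on a correlation stated for one trial and applied to the other two. That also stands. A reader might conclude that half the precision is lost. This is true only of inverse variance, for a single post-module score, at r = .7. At r = .34 the variance falls by about 12%. The gain shrinks with r but is present at every value checked.

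A third reply is that chance imbalance does not bias a randomized comparison, and that a correct standard error already allows for it. This stands too, so imbalance should not be counted as a loss on top of the power figures. Nor does adjustment remove it: the site-level part depends on a site-level correlation that nobody knows, and a cluster term is still needed.

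Finally, because 7.2.1 says that "experimental condition providers received their training in the SPSHK module" before parents are assessed, a reader might infer that module content leaks to parents before T2. Nothing in the documents reports this, and 7.2.4 places delivery after T2. The argument is speculative and forms no part of this point.

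**Conclusion.** The point holds as a better method available at no cost. Section 8.3 should specify T1 as a covariate for the between-arm comparison and does not. At the planned 62 per arm, with d = .45, one post-module score and clustering ignored, adjustment takes power from 70% to between 75% and 94% for correlations from .34 to .7. At .5 it already decides whether that comparison meets the plan's 80% target.

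The test the plan says it is powered for is not a safe fallback. Its 80% requires the full .45 as the difference averaged over all four occasions. If .45 appears only at T3 and T4, power is about 29% at a correlation of .7.

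These figures compare methods and do not forecast the trials' power. Absolute power will be lower with site clustering, by an amount that cannot be fixed without the number of sites and the ICC. It would be wrong to infer that adjustment alone secures 80%: under the assumed 8-site case it reaches about 55%.

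**What to change.** In 8.3:

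- Delete the simple t-test for the between-arm comparison.
- State that the arm difference in post-module Module Assessment scores (T3 and T4) is estimated with the parent's T1 score as a covariate, in the same model that accounts for the randomized cluster.
- Name that cluster. Section 7.1 randomizes sites, while 17.1 describes randomizing facilitators; the two need to be reconciled before the model can be written.
- State which of T3 and T4 is primary, since neither 1.2 nor 8.3 does.
- Replace the sentence about being powered for between-factors ANOVA with one that refers to the chosen model.

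The T1-adjusted arm difference at T2 may be reported as an optional check.

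The cost is wording only. T1 is already collected, so no added visits, instruments or participants are needed.
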